## 1. PROTOCOL SYNOPSIS

Study Number	UCI 23-107
Study Title	Empowering patients' Lung Cancer Screening uptake (Empower LCS)
Development Phase	II
Funding Source(s)	Anti-Cancer Challenge Pilot Award
Operational Changes during the COVID-19 Pandemic	N/A
Sources of Study Drugs	N/A
Number and Identity of Study Sites	University of California Irvine Health
Study Rationale	Utilization of lung cancer screening (LCS) using Low Dose CT (LDCT) among those eligible is low. We are assessing feasibility of a multi-level intervention to improve lung cancer screening uptake.
Study Design	Single arm longitudinal study
Study Objectives	
 
1. Assess feasibility of our multi-level intervention in increasing patients' LCS knowledge, having a LDCT ordered, and patients' receipt of LCS with LDCT.
 
2. Assess LCS-eligible patients' and their providers' perceptions and barriers towards LCS.
 
3. Describe patients' & providers' experience with the intervention using a mixed-methods approach.
 

Planned and Maximum Sample Size	70 patient participants (English, Spanish, and Vietnamese speaking), and between 20-40 non-patient participants.
Duration of Study Participation	
Patient participants: 6 months. Up to 15 patients will be asked to participate in a 30-min interview after 6 months completion of the study.
 
Non-patient participants: One time. 5 non-patient participants will be asked to participate in a 30-min interview within 3 months of last patient enrollment.

Indication(s) Under Study	Patients eligible for lung cancer screening
Inclusion Criteria	
 
1. Aged 50- 80 years of age.
 

	
 
2. Be able to Speak English, Spanish, or Vietnamese
 
3. Must have a primary care provider
 
4. Meeting the LCS eligibility criteria based on self-reported smoking history (for UCI and non-UCI Health patients) as well as documented in EMR (for UCI Health patients) and confirmed prior to enrollment
 

Exclusion Criteria	
 
1. No prior history of lung cancer
 
2. No chest CT for any reason in the last 12 months based on self-report (for UCI and non-UCI Health patients) and UCI EMR (for UCI Health patients)
 
3. No history of Alzheimer's disease or dementia
 

Study Intervention	Our proposed intervention, informed by the Health Belief Model  , is a multi-level intervention including: (1) PCP notifications of patients' LCS eligibility (addressing provider time constraints and barrier in identifying eligible patients); (2) patients' education (addressing knowledge barriers); (3) patients' referral to financial navigation resources (addressing health-related social risks); and (4) patients' reminder to discuss LCS during PCP visit.
Baseline Assessments	Baseline survey at enrollment
Efficacy Assessments	Follow-up survey 6 months after enrollment
Statistical Methodology	Descriptive measures, comparison of pre- and post- intervention endpoints
Efficacy Endpoints	Primary end point is order of LDCT within 6 months after enrollment assessed with self-reported surveys (for UCI and non-UCI Health patients) and EMR data extraction (for UCI Health patients)

**Figure 1 Study Schematic**

**A. Pre-Screening (identify potentially eligible population)**

UCI Health IT Enterprise will be queried for a list of patients 50-80yrs of age and speak English, Spanish, and Vietnamese. If they have a history of smoking or an unknow history of smoking and have a Primary Care Provider. Primary care clinics list of patients and EMR will also be manually checked for potential eligible patients. We will also distribute study flyers to community clinics and Vietnamese and Spanish speaking social media, and news outlets.

**B. Screen/Approach Patients:**

Approaching all potentially eligible patients via Redcap survey, phone, mail or in person in the clinic:

- Verify study eligibility by a short 2-minute survey.
- Recruit eligible subjects for participation.

**C. Consent Patients:**

Obtain written informed consent (DocuSign or paper).

**D. Baseline Procedures**

Encourage participants to complete baseline survey.

**E. Deliver Interventions**

(1) PCP notifications of patients' LCS eligibility; (2) patients' education; (3) patients' referral to financial navigation resources; and (4) patients' reminder to discuss LCS during PCP visit.

**F. Follow up Procedures:**

Participants complete a follow-up survey 6 months post-enrollment.

Non-patient participants (Primary Care Providers) will complete a survey

**G. Qualitative Interview**

15 patients will be randomly selected to undergo a 30-minute interview.

5 providers with highest number of enrolled patients in the study will undergo a 30-minute interview

**Table 1 Schedule of Events**

	Pre-Screen	Screen	Baseline	Primary Care Appointment	6 months Follow-up	Provider Survey	Interview
UCI Health IT inquiry	X						
Distribution of flyer to community clinics and Spanish and Vietnamese speaking social media and news outlet	X						
Screening 2-min survey		X					
Informed Consent			Prior to PCP appointment				
Baseline Survey			After informed consent prior to PCP appointment				
Intervention delivery				After baseline survey, prior to PCP appointment			
Follow-up survey					Within -14 and +30 days of 6 months follow-up		
Provider Survey						Within 3 months of last patient enrollment	
Interview							Within 30 days of patient or provider completion of their survey.

## 2. ABBREVIATIONS AND ACRONYMS

Abbreviation	Definition
AE	Adverse Event
CT	Computed Tomography
CTCAE	Common Terminology Criteria for Adverse Events
DSMB	Data and Safety Monitoring Board
EMR	Electronic Medical Record
HRPP	Human Research Protections Program
LCS	Lung Cancer Screening
LDCT	Low Dose CT
NCI	National Cancer Institute
SAE	Serious Adverse Event
USPSTF	United States Preventive Services Task Force

### 3. BACKGROUND AND RATIONALE

Lung cancer is the leading cause of cancer-related mortality, with 1.8 million annual deaths worldwide. Lung cancer screening (LCS) with low-dose computed tomography (LDCT) is shown to decrease mortality rate of lung cancer by 20%, compared with chest x-ray alone. From 2015, both private and public health insurance began to cover lcs with ldct. However, lcs uptake remains low, with only 12.8% of LCS-eligible patients receiving ldct in 2019, and 55% of those with a baseline LDCT returning for ldc in the subsequent 12-36 months. Further, white race is twice more likely to be adherent to lcs compared to races other than white. The 2021 US Preventive Service Task Force (USPSTF) update expanded the eligibility criteria and recommended high-risk populations (aged 50–80 years old, have a 20 pack-year smoking history, and currently smoke or have quit within the past 15 years) to receive annual LDCT to screen for lung cancer.

There are several barriers to LCS. **Provider barriers** includes the failure of the electronic medical record (EMR) to notify providers of eligible patients (most common), patient refusal, perceived high false-positive rate leading to unnecessary procedures, provider time constraints, and patients' lack of insurance coverage. Identifying eligible patients through EMR is often challenging as smoking pack-year data is either not complete or discordant (92.6% in one study) with patients' self-reported data obtained during patient-provider shared decision making conversations regarding LCS. This results in lack of trust of the primary care providers (PCP) to use EMR data for such purposes. **Patients' barriers** to LCS includes concerns regarding insurance coverage and co-pay for both screening and treatment (if diagnosed with cancer), access to convenient care, fear of a positive screening result or radiation exposure, and lack of understanding that lung cancer correlates with smoking history. Prior research assessing perceptions and barriers towards LCS and interventions to address barriers among diverse non-white and non-English-speaking population is limited. Interventions addressing LCS knowledge barriers have shown an increase in patients' knowledge or decisional certainty, but were not sufficient to increase receipt of LCS. On the other hand, interventions involving direct patient outreach (e.g., reminders to call and schedule LCS) or patient navigators addressing multiple barriers were more successful in increasing LCS uptake.

**Our proposed intervention**, informed by the Health Belief Model, is a multi-level intervention including: (1) PCP notifications of patients' LCS eligibility (addressing provider time constraints and barrier in identifying eligible patients); (2) patients' education (addressing knowledge barriers); (3) patients' referral to financial navigation resources (addressing health-related social risks); and (4) patients' reminder to discuss LCS during PCP visit. We propose to assess perceptions and barriers towards LCS and test our intervention among 0 English-, Spanish- and Vietnamese-speaking LCS-eligible patients with a scheduled PCP visit at any of UCI primary care clinics including FQHC or at non-UCI Health clinics in the next five months.

#### 4. STUDY OBJECTIVES

##### 4.1. Primary Objective

4. Assess feasibility of our multi-level intervention in increasing patients' LCS knowledge, having a LDCT ordered, and patients' receipt of LCS with LDCT.

##### 4.2. Secondary Objectives

1. Assess LCS-eligible patients' and their providers' perceptions and barriers towards LCS.
2. Describe patients' & providers' experience with the intervention using a mixed-methods approach.

#### 5. INVESTIGATIONAL PLAN

##### 5.1. Indications Under Study

Patients eligible for lung cancer screening

##### 5.2. Overall Study Design

We will conduct a single arm longitudinal clinical trial of 70 LCS-eligible patients with a PCP appointment at UCI health within five **months** after enrollment. All patients will complete a baseline survey to assess their perceptions and barriers towards LCS and will receive a multi-level intervention. All patients will complete a survey at 6 months post-enrollment to assess changes in perceptions and knowledge, receipt of an order for LDCT or completion of LDCT, and experience with intervention. All primary care providers of enrolled patients will be sent a survey 3 months after last patient enrollment to assess providers' barriers to order LCS. We will interview randomly selected up to 15 patients and 5 PCP participants with highest enrolled patients in the study, who consent to be interviewed to assess experience with the intervention.

##### 5.3. Study Segments and Visits

The different phases of the study are illustrated in [Figure 1](#), with details of assessments schedule in the main study segments given in [Table 1](#).

##### 5.4. Number of Subjects

70 patient participants, and between 20-40 non-patient participants.

### **5.5.        Definition of Completers**

Participants who complete all study procedures are considered completers. For patients this include consenting, completing baseline survey, receiving study intervention and completing the 6 months follow-up survey.

### **5.6.        Study Stopping Rules**

Not applicable.

## 6. STUDY POPULATION

### 6.1. Inclusion Criteria

Patients with the following characteristics are eligible for enrollment into the study:

Aged 50- 80 years of age.

Be able to Speak English, Spanish, or Vietnamese

Must have a Primary Care Providers.

Meeting the LCS eligibility criteria based on self-reported smoking history as well as documented in EMR and confirmed prior to enrollment (current or former smoker with 20 pack year smoking history)

### 6.2. Exclusion Criteria

The following patients will not be eligible for participation in the study:

No prior history of lung cancer

No chest CT for any reason in the last 12 months based on self-report (for UCI-Health and non-UCI Health patients) and UCI EMR (for UCI-Health patients)

No history of Alzheimer's disease or dementia

## 7. STUDY PROCEDURES

### 7.1. Pre-Screening

*UCI Health Patients:*

UCI clinical data warehouse will be inquired every week for a list of patients and their contact information, who are 50-80 years old, speaking English, Spanish or Vietnamese, and have a primary care provider, who are current or former smokers or have an unknown smoking history in EMR, and have no history of lung cancer, Alzheimer's disease or dementia, and have not received a chest CT or LDCT in the last 12 months. We will further inquire from primary care providers about their potentially eligible patients. EMR will also manually be reviewed to assess eligibility and generate an additional list for recruitment. We will take a note of patients with primary care appointment in next 5 months so that we have in person outreach.

We will send an email outreach with the study information, an option to opt out if not interested, and a short 2-min REDCap survey to verify LCS eligibility if interested in participating. For non-English speaking patients, the email outreach and survey will be sent in their preferred language. The survey includes questions on smoking history, prior history of lung cancer, and prior receipt of chest CT in the last 12 months.

To ensure our sample size is representative of population, we plan to have phone outreach, text message outreach, in person clinic visits to directly recruit participants, or mailing surveys (by bilingual research team) to patients who do not have an email address or do not respond to the email outreach, a common condition among non-English speaking patients.

#### *Non-UCI Health patients*

Additionally, we will conduct outreach to patients outside of the UCI Health system.

Outreach materials, such as flyers with QR codes, will be distributed to local clinics serving Latino and Vietnamese populations to be placed in their waiting rooms. We will also distribute these flyers via social media groups aimed at Spanish- and Vietnamese-speaking population. Lastly, working with cancer center community outreach program we distribute the flyers during community events. We may advertise the flyers with 1-2 message during local radio or TV outlets.

Patients who are interested will scan the QR code to easily connect with our team. They can also call us or email us if interested. We will also provide drop-off boxes in the clinics for interested patients to leave their contact information.

The 2-minute pre-screening survey for non-UCI Health patients will include inquiring about the name and contact information for their primary care doctor.

Non-UCI Health providers will not be engaged with human subject research at any point.

#### **7.2. Non-eligible patients**

Patients who do not meet the eligibility criteria based on the survey will be asked to complete a HIPAA authorization form sent to them via DocuSign, fax or mail, based on patients' preference.

Given documenting smoking history in EMR during health encounters is being implemented at UCI, we plan to compare EMR smoking history data with patients' self-report to assess for accuracy. This only applies to UCI Health patients.

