**Table 2 . Study Outcomes, Measures and co-variates**

Efficacy Outcomes		
LDCT order for LCS	6 mo	Survey and EMR
Receipt of LDCT for LCS	6 mo	Survey &EMR
Pt and PCP LCS discussion	6 mo	
Pt perceived risks, benefit, barriers, and self-efficacy using LCS health belief mode 	Baseline & 6 mo	Survey
Process Evaluation Outcomes		
Rate of concordance of EMR and self-report smoking hx	Baseline	Survey& EMR
Showing up to PCP visit	6 mo	
Self-referral to PAF	6 mo	Survey
Pt and provider experience with intervention components	6 mo	Survey& interview
Provider perceived barriers and knowledge of LCS	Beginning 9 mo after first pt enrollment	Survey
Covariates		
Sociodemographics, insurance, neighborhood deprivation index, health literacy, comorbidities	Baseline	Survey
Financial worry  and health-related social risks 	Baseline & 6mo	Survey

- Any mention of ER is only for UCI Health patients.

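### As written, UCI patients who report eligible smoking that the EMR does not show have almost no route into the EMR versus self-report comparison, so EMR misses could not be properly estimated

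*Combined protocol and SAP*

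**What the plan says.** Table 2 lists "Rate of concordance of EMR and self-report smoking hx" as a baseline process outcome, and Section 10.4 promises to report it. Section 7.2 gives the purpose: "we plan to compare EMR smoking history data" against self-report, for UCI Health patients only, to judge accuracy. None of the three places defines the unit compared, the metric or the denominator.

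The documents describe two ways for a UCI patient to supply paired data.

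- **Not enrolled.** Section 7.2: "Patients who do not meet the eligibility criteria based on the survey will be asked to complete a HIPAA authorization form". Patients who pass the survey go to the consent call (Section 7.3).
- **Enrolled.** The Synopsis requires eligibility by self-reported smoking history "as well as documented in EMR (for UCI Health patients) and confirmed prior to enrollment". Section 6.1 has the same rule: "Meeting the LCS eligibility criteria based on self-reported smoking history as well as documented in EMR and confirmed prior to enrollment". Section 11.3 asks for both the survey and UCI Health IT data as source documents for eligibility.

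Section 7.1 sets the frame. The weekly query draws patients "who are current or former smokers or have an unknown smoking history in EMR", so patients recorded as never smokers are not drawn. Two further routes add names: manual EMR review and provider inquiry ("We will further inquire from primary care providers about their potentially eligible patients").

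**The concern.** The two entry routes between them select on agreement. A patient who reports qualifying smoking, but whose EMR is incomplete or falls below the criterion, has passed the survey and so gets no form under Section 7.2. The same patient fails the EMR half of the inclusion criterion and so is not enrolled. A patient who passes both checks but declines the trial is not asked for authorization either.

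The group left out is the one of most interest. Section 3 names the EMR's failure to alert providers to eligible patients as the most common provider barrier, and cites one study in which 92.6% of EMR pack-year data were incomplete or discordant. A comparison that hardly admits the patients whom the EMR misses cannot measure how often it misses them. Choosing a denominator at the analysis stage does not help, because data that were never authorized cannot be recovered.

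**Working it through.** The plan states no expected concordance or accuracy, so there is no figure to reproduce. All cell values below are assumptions, used to show direction and size.

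**Cells.** Take UCI patients who complete the survey, with self-report as reference. An unknown EMR history counts as not showing eligibility.

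| | EMR shows eligibility | EMR does not |
|---|---|---|
| Self-report eligible | a | b |
| Self-report not eligible | c | d |

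**Step 1: who enters, read literally.** Cell a enters by enrollment if the patient consents. Cells c and d enter through the Section 7.2 form if it is returned. Cell b is sent no form and fails the inclusion criterion.

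**Step 2: sensitivity.** True sensitivity is a/(a+b). With b absent it reads a/a = 100%. Negative predictive value, truly d/(b+d), reads d/d = 100%.

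**Step 3: concordance.** Let p be the share eligible by self-report, Se the EMR sensitivity and Sp its specificity. Let r1 be the entry rate in cell a, and r2 the entry rate in cells c and d.

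- True concordance = (a+d)/(a+b+c+d) = p·Se + (1−p)·Sp
- Observed concordance = (r1·a + r2·d)/(r1·a + r2·(c+d))

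Per 100 surveyed, with p = 50%, Sp = 80% (c = 10, d = 40) and r1 = r2:

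| Se | a | b | True | Observed |
|---|---|---|---|---|
| 30% | 15 | 35 | 55/100 = 55.0% | 55/65 = 84.6% |
| 50% | 25 | 25 | 65/100 = 65.0% | 65/75 = 86.7% |
| 70% | 35 | 15 | 75/100 = 75.0% | 75/85 = 88.2% |
| 90% | 45 | 5 | 85/100 = 85.0% | 85/95 = 89.5% |

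True concordance ranges over 30 points. The observed figure moves by about 5.

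**Step 4: is the direction certain?** Observed concordance is a weighted average of 1 and Sp, so it is never below Sp. True concordance is a weighted average of Se and Sp, so it is at most Sp when Se ≤ Sp. In that case there is no understatement at any entry rates. With equal entry rates there is inflation whenever b > 0. When Se > Sp and enrolled patients enter at a lower rate, the direction can reverse. With p = 50%, Se = 90%, Sp = 50%, r1 = 0.2 and r2 = 0.8, the cells are a = 45, b = 5, c = 25, d = 25. True concordance is 70/100 = 70.0%. Observed is (9+20)/(9+40) = 29/49 = 59.2%.

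**Step 5: the never-smoker exclusion.** Assume 1,000 patients. Of these, 600 are EMR never-smokers (20 eligible by self-report), and the other 400 have a/b/c/d = 80/60/60/200.

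- Whole population: (80+200+580)/1,000 = 86.0%
- Queried frame: 280/400 = 70.0%
- Planned sample: 280/340 = 82.4%

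The same sample figure is too high for the queried frame and too low for the whole population. Population sensitivity is 80/(80+60+20) = 50%, and it still reads 100%.

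**The case against.** Four counter-arguments have substance.

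1. **The literal rule may not be the practice.** Section 7.1 deliberately recruits patients whose EMR smoking history is unknown. Section 7.6 makes the usual-care EMR flag for consented patients conditional on a complete smoking history, which implies that some enrolled patients lack one. If staff enroll on self-report, cell b is partly filled. This stands: a reader might infer that such patients cannot enter at all, and the documents do not support that. They conflict, and whether the cell fills depends on practice that is not written down.

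2. **There is a side door.** The survey also asks about prior lung cancer and recent chest CT. A patient who reports qualifying smoking but fails on one of these gets the Section 7.2 form, and may have an EMR that misses the smoking. This stands too, so the result is near 100%, not exactly 100%. The route is probably small, because the query already removes recorded lung cancer and recent CT. Patients who enter this way do not represent those missed.

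3. **The plan promises concordance, not sensitivity.** Sensitivity is nowhere named, and disagreement on pack-years among enrolled patients stays observable. That is fair. But Section 7.2 speaks of accuracy, and missed eligibility is the EMR failure that Section 3 stresses. Leaving the metric undefined does not restore the missing patients.

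4. **Authorization may be wider than it looks.** The consent documents were not available for this review, so what a patient authorizes on signing cannot be checked. Section 7.2 also does not say that the comparison is confined to the two groups above. This lowers certainty, but gives no stated route for decliners.

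A reader might also infer that EMR accuracy must come out overstated. Steps 4 and 5 show that this is not so for overall concordance.

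**Conclusion.** The concern holds in a limited form. If the both-sources criterion is applied as written, patients eligible by self-report but not by EMR have almost no route into the comparison, and survey-eligible decliners have none stated. EMR sensitivity for eligibility would look near perfect whatever its true value, so missed-eligible error could not be properly estimated.

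Within the surveyed frame, concordance is inflated whenever EMR sensitivity is at or below specificity, and under equal participation whenever any eligible patient is missed. The example of 75.0% reading 88.2% rests on assumed values (50% eligible by self-report, 70% sensitivity, 80% specificity, equal participation), and none of them comes from the documents. With sensitivity above specificity and unequal entry, concordance can be understated.

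If enrollment in practice follows self-report, the gap narrows to decliners and to EMR never-smokers outside the query. This is one process outcome in a 70-patient feasibility study. The primary endpoint, LDCT order within 6 months, is untouched, but the change is cheap enough to be worth making.

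**What to change.** - **Section 7.2:** request HIPAA authorization from every UCI patient who completes the 2-minute survey, whatever the eligibility result and whether or not the patient joins the trial.
- **Section 10.4:** state the unit compared and the denominator. Report the full table of EMR status (eligible, not eligible, unknown) by self-report status (eligible, not eligible) over all authorized completers.
- **Interpretation:** describe the result as agreement among patients recorded in the EMR as current, former or unknown smokers, not as EMR accuracy in general, because the weekly query leaves out recorded never smokers.
- **Reconcile** the inclusion criterion (Synopsis, Sections 6.1 and 11.3) with Sections 7.1 and 7.6 on whether a UCI patient with an incomplete or unknown EMR smoking history can enroll.

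The cost is a few protocol sentences, some extra authorization requests and some extra chart look-ups. The change to Section 7.2 has to be made before or during recruitment. Authorization will still be voluntary, so the report should also give the number surveyed and the number authorized in each self-report group.
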